#### Funding Body

No external funding sought. Study is supported by A&E and Biochemistry departments of NHS Greater Glasgow and Clyde

# ABBREVIATIONS

A&E	Accident and Emergency
AE	Adverse event
CRF	Case Report Form
ED	Emergency Department
FAST	Fast Alcohol Screening Test
GMAWS	Glasgow Modified Alcohol Withdrawal Scale
GRI	Glasgow Royal Infirmary
IV	Intravenous
REC	Research Ethics Committee
SAE	Serious Adverse Event
SmPC	Summary of Product Characteristics
ТКА	Transketolase
WE	Wernicke's Encephalopathy

# **STUDY SYNOPSIS**

Title of Study:	Effect of Magnesium and Thiamine on red cell	
	transketolase activity	
Study Centre:	Glasgow Royal Infirmary	
Duration of Study:	12 months	
Primary Objective:	Does magnesium administration enhance the biochemical response to thiamine as measured by the activity of the enzyme transketolase in red blood cells?	
Secondary Objective:	
 
What is the effect of the administration of thiamine alone,
 
Magnesium alone, or both together on
 
Plasma lactate concentrations
 
Biomarkers of ageing
 
	
Primary Endpoint:	Change in erythrocyte transketolase activity after treatment with - Thiamine - Magnesium - Thiamine plus magnesium	
Rationale:	Chronic alcoholics have a 30-80% incidence of thiamine deficiency causing Wernicke's Encephalopathy (WE). Intravenous (IV) thiamine replacement is standard practice in the treatment of alcoholic patients presenting to the Accident & Emergency (A&E) department, however routine co-supplementation with magnesium (administered IV as magnesium sulphate ), a co-factor for thiamine in some metabolic processes, e. g. on the activity of the enzyme transketolase in red blood cells, is not routine practice in the treatment of these patients. Without correction of concomitant magnesium deficiency there may be impaired utilisation of thiamine resulting in a failure to treat WE. This study is designed to determine if administration of Magnesium to alcoholic patients affects red cell transketolasae by itself, or only acts to increase the effect of thiamine on the activity of this enzyme.	
Methodology:	Open label, randomised controlled study	
Sample Size:	120	
Screening:	Confirmation of chronic alcoholism (FAST questionnaire. GMAWS score)	
Registration/Randomisation:	Randomisation will be performed using individually numbered opaque envelopes.	
Main Inclusion Criteria:	Chronic alcohol dependence	
Main Exclusion Criteria:	Known chronic renal failure	
Product, Dose, Modes of	Participants will be randomised to:	
Administration:	• Arm 1:Thiamine	
	
 
Arm 2: Thiamine and magnesium sulphate
 
Arm 3: Magnesium sulphate with delayed thiamine where thiamine will be administered as Pabrinex.
 
	
Duration of Treatment:	Each infusion will be administered over 30 minutes	
Statistical Analysis:	A three group study was designed to detect a minimum biochemically significant difference of 0.16 in the change from baseline between the groups, with 80% power and a 5% significance level. total sample size = 120. Methodology: One way ANOVA	

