# 3. STUDY DESIGN

This is a 3- arm randomised, open label, controlled study in a cohort of alcoholic patients admitted through A&E. Patients will be randomised to concurrent infusion of one of the following:

- Arm 1: IV thiamine
- Arm 2: IV magnesium sulphate followed by delayed IV thiamine
- Arm 3: IV thiamine and IV magnesium sulphate

Thiamine will be administered as IV Pabrinex, a compound preparation which also contains B vitamins and vitamin C. Administration of IV Pabrinex is standard care in this patient group and magnesium sulphate is routinely co-administered at Glasgow Royal Infirmary.

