# 3.1 Study Population

A total of 120 patients will be recruited to this study, with 40 being randomised to each arm i.e.

- Arm 1: IV thiamine (Pabrinex)
- Arm 2: IV magnesium sulphate followed by delayed thiamine (Pabrinex)
- Arm 3: IV thiamine (Pabrinex) and IV magnesium sulphate

Patients will be identified by ED staff on presentation to the ED.

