#### Part 2: Administration of study medicines

Patients will be randomised to one of the following regimes and infusions administered:

• Arm 1: IV thiamine (Pabrinex)

- Arm 2: IV magnesium sulphate and delayed Pabrinex
- Arm 3: IV thiamine (Pabrinex) and IV magnesium sulphate

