## Part 4: Administration of delayed Pabrinex (Arm 2 only)

For patients randomised to Arm 2, (IV magnesium sulphate and delayed thiamine), Pabrinex will be administered after the second blood samples have been taken, approximately 2 hours (+/- 30mins) after completion of magnesium sulphate infusion.

Case report forms will be updated as appropriate.

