# 6. DRUG INFORMATION

Patients who are eligible for the study will be randomised to receive one of the following arms:

- Arm 1: IV thiamine (Pabrinex)
- **Arm 2:** IV magnesium sulphate followed by delayed thiamine (Pabrinex) administered after completion of post-intervention assessments.
- Arm 3: IV thiamine (Pabrinex) and IV magnesium sulphate

In Arm 3 IV Pabrinex and IV magnesium sulphate will be administered concurrently. There is limited data available on Y-site compatibility for Pabrinex and magnesium sulphate infusions

however, it has been standard practice at GRI to administer in this way for a number of years.

All study drug administration will be completed within the ED where full resuscitation facilities are available.

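### Does the synopsis's reversed numbering of Arms 2 and 3 put treatment allocation or the primary comparison at risk?

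*Combined protocol and SAP*

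**What the plan says.** The treatment entry of the Study Synopsis gives thiamine as Arm 1, then "Arm 2: Thiamine and magnesium sulphate", then "Arm 3: Magnesium sulphate with delayed thiamine where thiamine will be administered as Pabrinex".

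The body keeps Arm 1 as thiamine and reverses the other two:

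- Section 3 has "Arm 2: IV magnesium sulphate followed by delayed IV thiamine", with the combination as Arm 3.
- Section 3.1 uses the same order and plans 40 patients per arm.
- Section 4.3 Part 2 has "Arm 2: IV magnesium sulphate and delayed Pabrinex", again with the combination as Arm 3.
- Section 4.3 Part 4 confines delayed Pabrinex to Arm 2 in its heading. Its text opens with "For patients randomised to Arm 2, (IV magnesium sulphate and delayed thiamine", so the regimen follows the number in brackets.
- Section 6 lists all three arms with their regimens and then says: "In Arm 3 IV Pabrinex and IV magnesium sulphate will be administered concurrently".

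Section 4.2 says the envelopes show the subject number and the treatment allocation. It does not say whether the allocation appears as a number, a treatment name or both.

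**The concern.** An arm number should have one meaning throughout a protocol, and here Arms 2 and 3 each have two. Two instructions are tied to those numbers: who has Pabrinex held back until after the second blood sample, and who has both infusions together. Someone who took the key from the synopsis and the instruction from the body would apply each to the wrong group.

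The pair is also an awkward one to confuse. Both arms receive the same two products once each, so a bare list of drugs given would look alike. What separates them is whether Pabrinex comes before or after the 2-hour sample, and therefore whether that sample reflects the combination or magnesium alone. The primary objective asks whether magnesium enhances the response to thiamine, and the comparison that answers it is combination against thiamine. If the labels of Arms 2 and 3 were exchanged in the dataset, that comparison would be credited to the wrong group. The overall one-way ANOVA would not reveal it, because the overall F statistic does not depend on what the groups are called.

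**Working it through.** **Step 1. The definitions side by side.**

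| Place | Arm 2 | Arm 3 |
|---|---|---|
| Study Synopsis | combination | magnesium first, thiamine later |
| Section 3 | magnesium first, thiamine later | combination |
| Section 3.1 | magnesium first, thiamine later | combination |
| Section 4.3 Part 2 | magnesium first, thiamine later | combination |
| Section 4.3 Part 4 | magnesium first, thiamine later | (not mentioned) |
| Section 6 | magnesium first, thiamine later | combination |

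The count is one place against five. Every list is complete and readable, so text extraction or redaction does not explain the difference.

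**Step 2. Does any instruction need the synopsis to be understood?** Section 4.3 Part 2 names each regimen at the point of administration. Part 4 gives the regimen beside the number. In section 6 the sentence on concurrent infusion follows directly on the list of arms and itself names both drugs. A person following these sections never has to look up a number elsewhere.

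**Step 3. Does the analysis use arm numbers?** Section 2, the primary outcome (4.4.1) and the secondary outcomes (4.4.2) all identify groups by treatment.

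**Step 4. Does any figure depend on the numbering?** Inputs: difference 0.16, power 80%, significance level 5% (section 8.1); the higher pilot standard deviation, 0.2176 (section 8.2); three groups. Assume the extreme means are 0.16 apart and the third lies midway. The squared deviations of the means then sum to 0.16²/2 = 0.0128. The noncentrality parameter of the one-way ANOVA is

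λ = n × 0.0128 / 0.2176² = n × 0.0128 / 0.04735 = 0.2703 n.

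- n = 36: λ = 9.73, power 0.792.
- n = 37: λ = 10.00, power 0.804.

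The stated 37 per arm reproduces. At the planned 40 per arm, power is 0.836. Arm numbers do not enter, and the arms are equal in size, so exchanging two labels alters nothing here.

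**Step 5. Would an exchange go unnoticed?** Section 3 says Pabrinex also supplies other B vitamins and vitamin C. Section 4.3 has vitamins B1, B2, B6 and C measured at baseline and at 2 hours, and the magnesium-first arm receives Pabrinex only after the second sample. If the two labels were wholly exchanged, the group called combination should show no rise from Pabrinex at 2 hours, and the group called magnesium should show one. For individual patients, section 6.2 has treatment prescribed on the Kardex and its administration documented, and section 4.2 keeps the opened envelope with the case report form.

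**The case for a change.** The strongest case for action is that the safeguards lie in the protocol text, while the exposure lies in materials we cannot see. Section 4.2 does not say how the envelope expresses the allocation, section 10 gives no coding for the case report form, and nothing in the document says the body prevails over the synopsis. If a bare number were used anywhere, the consequence could be large. Take the pilot means in section 8.2 as changes in transketolase activity, although the table does not label them so. The combination-minus-thiamine difference is then 0.3211 − 0.1433 = 0.1778. Under a complete label exchange it becomes m − 0.1433, where m is the mean change on magnesium alone. The documents do not give m. The result would be −0.1433 if m = 0, zero if m = 0.1433, and still 0.1778 if m = 0.3211.

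That arithmetic is right, and it is true that the ANOVA would not expose a full exchange. But it describes what an exchange would do, and offers no evidence that the numbering slip would cause one. Two unsupported steps are needed: a number without a treatment name on the working materials, and a reader who decodes it from the synopsis alone against five consistent places in the body. The documents support neither step. Partial exchanges could be tabulated as well, but the number exchanged would be invented. Comparing the results with 0.16 would also mean little, because 0.16 is the difference used for sample size and not a threshold for success.

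What stands is that the two numberings conflict and that nothing in the text settles which is meant.

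**Conclusion.** This is a clerical slip that calls for no change to the plan. One synopsis entry is out of step with five places in the body. The numbering must be reconciled to one definition per arm when the document is next edited, and it is sensible for the randomisation list and envelopes to be read against that definition. Which numbering is right is for the sponsor to say. The correction alters no regimen, outcome, sample size (37 required and 40 planned per arm) or analysis.

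The conclusion rests on three things. Staff administer treatment from sections 4.3 and 6, where the regimen is named. Treatment is open label, and the Kardex record is taken to show when each infusion was given. The vitamin samples before and after treatment would probably show a wholesale exchange of labels. The documents contain no sign that any patient was misallocated.

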# **1.3 Study hypothesis**

Hypothesis: That magnesium administration enhances the biochemical response to thiamine.

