#### • Primary Objective

To determine whether Magnesium administration enhances the biochemical response to thiamine as measured by the activity of the enzyme transketolase in red blood cells

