## 3.5 Assessment and management of risk

As above, there are three arms to this study. Our previous study examined the effect of thiamine and magnesium, as compared to thiamine alone, on TKA activity. This demonstrated a significant increase in TKA activity in the magnesium and thiamine group as compared to the thiamine group. It is therefore necessary to include the magnesium sulphate arm to this study to confirm this effect was not directly attributable to Magnesium separately, and to elucidate the degree of synergism that may exist between magnesium and thiamine.

Alcoholism is a disease of malnutrition. Dietary deficiencies develop over weeks, months and years. We appreciate that the two hour delay to Pabrinex administration, represents a delay to standard treatment in the Magnesium group (with delayed Pabrinex). However there is no evidence in the literature to indicate that a real time delay of two hours may disadvantage a patient, or that a single treatment of Pabrinex can reverse the chronic changes associated with Vitamin B1 (Thiamine) deficiency. It is our view therefore that a two hour delay will not disadvantage the patients randomised to this group. Indeed a 2 hour delay is not uncommon in the Emergency Department (ED) for any treatment due to the acuity and volume of patients attending a busy inner city ED. All patients attending the ED should be treated and discharged within the 4 hour window, as dictated by the national access target for emergency care.

Patients will be identified at triage in order to ensure adequate time to recruit, consent and obtain repeat samples at the 2 hour time interval post administration of treatment whilst still meeting national targets. Eligible patients may therefore be seen earlier in their patient journey which may offset potential delays due to study involvement. The net effect will be that patients randomised to the Magnesium group, will therefore receive their Pabrinex at approximately the same point in their patient journey, as if the study were not ongoing.

Magnesium sulphate and pabrinex are routinely administered to this patient group in the ED at GRI.

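### The plan names only a one-way ANOVA and does not commit to the comparison, thiamine plus magnesium against thiamine alone, that tests its primary hypothesis

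*Combined protocol and SAP*

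**What the plan says.** Section 1.3 gives one hypothesis: "Hypothesis: That magnesium administration enhances the biochemical response to thiamine". The primary objective in section 2 repeats it: "To determine whether Magnesium administration enhances the biochemical response to thiamine", measured by red cell transketolase activity (TKA).

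The magnesium-only arm has a separate purpose. Section 3.5 says it is needed "to confirm this effect was not directly attributable to Magnesium separately" and to show the degree of synergism. The synopsis rationale asks whether magnesium affects the enzyme "by itself, or only acts to increase the effect of thiamine on the activity of this enzyme".

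That arm is sampled before it receives any thiamine. Section 4.3, Part 4 states that "Pabrinex will be administered after the second blood samples have been taken", and section 6 describes the arm as "IV magnesium sulphate followed by delayed thiamine (Pabrinex) administered after completion of post-intervention assessments".

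On analysis, the synopsis says "total sample size = 120. Methodology: One way ANOVA" and nothing more. Section 8.2 contains pilot descriptive statistics for two groups, combined and thiamine, and a repeat of the sample-size paragraph from 8.1. It gives no test, contrast, follow-up procedure, multiplicity rule or confidence interval. The 0.16 in 8.1 and 8.2 is a difference between the groups with no pair named. Section 4.4.1 lists the three treatments without a comparison.

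**The concern.** A one-way ANOVA model suits three arms, and the comparison of interest can be estimated within it. The difficulty is that its standard test, the omnibus F, asks whether all three means are equal. One arm has had no thiamine at the time of measurement, so a thiamine effect alone makes the means unequal. A significant F therefore says nothing specific about what magnesium adds to thiamine.

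If the ANOVA wording in the synopsis describes only the sample-size method, no primary analysis is stated at all, and the same remedy applies.

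What is at stake is pre-specification. As written, whether the key comparison stands alone or is one of three, which error term it uses, and whether it depends on F being significant first can all be settled after the data are seen. Nor does the plan say how the magnesium-only arm will answer the question that section 3.5 gives as the reason for including it.

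**Working it through.** **Inputs.** Pilot table in 8.2: combined, N 18, mean 0.3211, SD 0.2176; thiamine, N 12, mean 0.1433, SD 0.1214. Sections 8.1 and 8.2: difference 0.16, the higher SD, 80% power, 5% level, 37 per arm. Section 3.1: 40 per arm. Sidedness is not stated; two-sided is used here. The magnesium-only mean and SD are assumed, because the pilot had no such arm.

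**1. The plan's 37 per arm.** For the omnibus F with three groups, noncentrality λ = n Σ(mean − grand mean)² / SD². With means 0, 0.08 and 0.16:
- λ at 37 = 37 × (0.08² + 0.08²) / 0.2176² = 10.0, on 2 and 108 df; power 80.4%.
- At 36 per arm, power is 79.2%.

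So 37 is reproduced. A two-sided t test of one pair at alpha 0.025 also gives 37 (80.7%, against 79.4% at 36), so the source of the figure is not certain.

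**2. What F does when magnesium adds nothing.** Set both thiamine arms to 0.1433 and the magnesium-only arm to d. Then λ = n × (2/3) × (0.1433 − d)² / 0.2176². At 37 per arm, d = 0 gives λ = 10.7 and d = 0.08 gives λ = 2.09.

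| Assumed magnesium-only change d | F rejects, 37 per arm | F rejects, 40 per arm |
|---|---|---|
| 0 | 83% | 86% |
| 0.03 | 62% | 66% |
| 0.05 | 45% | 48% |
| 0.08 | 23% | 24% |

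**3. The direct comparison, thiamine plus magnesium minus thiamine alone.** With SD 0.2176 in both arms, SE = 0.2176 × √(2/n).
- 37 per arm: SE 0.0506, 0.16/SE = 3.16, 72 df; power 88%.
- 40 per arm: SE 0.0487, 0.16/SE = 3.29, 78 df; power 90%.
- With the two pilot SDs and a Welch test, power is 97% and 98%.
- With all three pairs co-primary under Bonferroni (alpha 0.05/3), power is 76% and 80%.

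**4. Which standard error.** If the pilot SDs hold, the true SE at 37 per arm is √((0.2176² + 0.1214²)/37) = 0.0410. The three-arm pooled SE depends on the magnesium-only SD, which is assumed:
- SD 0.1214: pooled SD √((0.2176² + 2 × 0.1214²)/3) = 0.160, SE 0.0372, type I error about 7.5%.
- SD 0.2176: pooled SD √((2 × 0.2176² + 0.1214²)/3) = 0.191, SE 0.0444, type I error about 3.4%.

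In simulation, Welch held about 5% in both cases. So did the ordinary two-sample t test, because the arms are equal in size.

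**5. The question in section 3.5.** If the untreated 2-hour change is about zero, two estimates bear on it, here with SD 0.2176:
- Magnesium-only within-arm change: 95% CI half-width t × 0.2176/√n = 0.073 at 37 and 0.070 at 40. A true change of 0.05 would be detected 27% and 29% of the time.
- Synergy, thiamine plus magnesium minus thiamine alone minus magnesium only: SE = 0.2176 × √(3/n) = 0.0620 and 0.0596. Power for 0.16 is about 73% and 76%.

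**The case against.** The strongest reply is that the pair of interest is already plain. The hypothesis and objective point to it, the previous study described in sections 1.2 and 3.5 compared those two treatments, and the pilot table in 8.2 has exactly those two groups, whose difference (0.3211 − 0.1433 = 0.178) is close to 0.16. This stands, and it limits how much freedom the investigator really has. It does not settle the error term, the multiplicity rule or the role of F, and the plan never says that this pair is the primary test.

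A reader might take 83%/86% as a false-positive rate for the primary claim. It is not. F is rightly rejecting equal means because thiamine works. It misleads only if F is read as evidence of enhancement, and no section says it will be. The rate also falls quickly as the assumed magnesium-only change rises.

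A reader might also infer that the trial is wrongly sized. The documents do not support that: 37 reproduces, and 40 per arm gives the direct comparison about 90% power.

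Nor is Welch the only valid choice. The two-sample t test also holds its level at equal arm sizes, and the 7.5% in step 4 needs an assumed SD. The unequal SDs come from groups of only 18 and 12.

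Finally, the direct comparison has its own limit. If magnesium alone raised TKA by 0.16 with no enhancement, it would still be significant 88% of the time at 37 per arm and 90% at 40. This stands, and it is why the two secondary estimates are needed.

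**Conclusion.** The point holds as a gap in specification. The one method named does not, by its omnibus test, address the primary hypothesis, and the comparison that does is indicated by the context but not committed to. With no magnesium effect, F would be significant between 23% and 83% of the time at 37 per arm (24% to 86% at 40) for magnesium-only changes between 0.08 and 0. This assumes thiamine-arm means of 0.1433 and a common SD of 0.2176.

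This should be fixed, but it is not a fatal flaw: the design, the data to be collected and the sample size already support the right analysis. Two neighbouring matters are separate points and are not argued here: the synopsis and section 3 number Arms 2 and 3 in opposite order, and section 4.4.1 refers to relative change. The first is a reason to name arms in words; section 3, for example, lists "IV magnesium sulphate followed by delayed IV thiamine" as Arm 2.

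**What to change.** In the synopsis and section 8.2:

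- **Primary analysis.** Name one: the difference in change in TKA from baseline to 2 hours, thiamine plus magnesium minus thiamine alone, two-sided 5%, with 95% CI. Take the standard error from those two arms (Welch, or the two-sample t test at equal n), not from the three-arm pooled variance.
- **Omnibus F.** Keep it as supportive.
- **Power.** State it for this comparison: about 88% at 37 and 90% at 40 per arm for 0.16 with SD 0.2176. The 37 per arm and the total of 120 stay.
- **Secondary, for the question in section 3.5.** Report, each with a 95% CI, the magnesium-only within-arm change and the estimate thiamine plus magnesium minus thiamine alone minus magnesium only. State that both assume an untreated 2-hour change of about zero, since there is no untreated arm, and that the second has only about 73% (37 per arm) or 76% (40 per arm) power for 0.16.

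The cost is wording; no extra patients, samples or procedures are needed. The downside is that comparisons involving the magnesium-only arm become secondary, which is for the sponsor to decide. If all three pairs are kept co-primary with Bonferroni, power for 0.16 falls to about 76% at 37 and 80% at 40 per arm, and the plan should say so.

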# 8.2 Statistical analysis plan

The following data was available from a pilot study for a two group design:

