#### **Descriptive Statistics: Combined, Thiamine**

 Variable
 N
 Mean
 SE Mean
 StDev
 Minimum
 Maximum

 Combined
 18
 0.3211
 0.0513
 0.2176
 0.0200
 0.7500

 Thiamine
 12
 0.1433
 0.0350
 0.1214
 0.0100
 0.4500

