#### Power and Sample Size

Choosing the higher st dev to be more conservative, a three group study was designed to detect a minimum biochemically significant difference of 0.16 in the change from baseline between the groups, with 80% power and a 5% significance level. This requires 37 participants to be randomised to each arm of the study. We therefore propose a total sample of 120 to account for any drop-outs or missing data.

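### The only planned analysis, one-way ANOVA, pools one variance over three arms; the combined-versus-thiamine comparison should be named and estimated with arm-specific variances, because a comparison on the pooled error term could have a type I error of about 2% to 11%, depending on a magnesium-only SD that is not given

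*Combined protocol and SAP*

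**What the plan says.** The Statistical Analysis entry of the Study Synopsis gives the method in one phrase: "Methodology: One way ANOVA". Section 8.2, although headed as the statistical analysis plan, contains only a pilot table and the sample-size text. Neither place names a contrast, a pairwise procedure, a multiplicity rule, a variance check or an unequal-variance alternative.

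The pilot table is introduced with "The following data was available from a pilot study for a two group design". It lists SD 0.2176 for combined treatment (n=18, mean 0.3211) and SD 0.1214 for thiamine (n=12, mean 0.1433). There is no magnesium-only row. The sample-size text then proceeds by "Choosing the higher st dev to be more conservative", targets a "minimum biochemically significant difference of 0.16 in the change from baseline between the groups", and concludes "This requires 37 participants to be randomised to each arm of the study". Section 3.1 sets the recruited numbers, "with 40 being randomised to each arm".

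The primary objective (section 2) asks whether magnesium enhances the response to thiamine. Sections 1.2 and 3.5 also ask whether magnesium acts on its own.

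**The concern.** The sizing text shows that the authors saw two different SDs, yet the named analysis assumes a single one. The omnibus F test does not answer the primary question, which is the difference between combined treatment and thiamine alone, so a two-arm comparison has to follow. In a one-way ANOVA the default standard error for such a comparison comes from the mean square pooled over all three arms. The standard error of combined minus thiamine then depends partly on how variable the magnesium-only arm is, although that arm plays no part in the difference.

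At stake is whether the p-value and confidence interval for the main result have their stated error rate. As written, that would depend on an SD that the plan does not have.

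**Working it through.** **Inputs.** Pilot SDs s_C = 0.2176 and s_T = 0.1214 (section 8.2 table); n = 37 per arm needed and 40 recruited (sections 8.1, 8.2 and 3.1); difference 0.16; two-sided 5% for pairwise tests (the plan does not state sidedness). The magnesium-only SD, s_M, is not in the documents and is varied from 0.02 to 0.25 as an assumption.

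**1. The plan's own figure reproduces.** Take three means at −0.08, 0 and +0.08 and a common SD of 0.2176. The noncentrality is 37 × (0.08² + 0.08²) / 0.2176² = 37 × 0.0128 / 0.04735 = 10.0. Omnibus F power is 80.4%, so 37 per arm is correct for that test.

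**2. How firm is the SD difference?** The variances are 0.04735 and 0.01474, with ratio 3.21. The F test on 17 and 11 df gives p = 0.054 and a 95% CI of 0.98 to 9.2. Unequal variances are suggested but not established, and equality is not established either.

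**3. Pooled against true standard error, equal arms.**
- True variance of combined minus thiamine: (s_C² + s_T²)/n.
- Pooled version: (2/n) × (s_C² + s_T² + s_M²)/3.
- Ratio of pooled to true SE: √[ (2/3)(s_C² + s_T² + s_M²) / (s_C² + s_T²) ], where s_C² + s_T² = 0.06209.
- The ratio is 1 when s_M² = (s_C² + s_T²)/2 = 0.03104, that is s_M = 0.176.

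**4. Type I error of the unadjusted pooled comparison** (simulation, normal data, 40 per arm; results at 37 per arm are within about 0.2 points).

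| s_M (assumed) | Pooled/true SE | Type I error, combined vs thiamine |
|---|---|---|
| 0.02 | 0.82 | 11.0% |
| 0.06 | 0.84 | 10.1% |
| 0.1214 | 0.91 | 7.5% |
| 0.1762 | 1.00 | 5.0% |
| 0.2176 | 1.08 | 3.4% |
| 0.25 | 1.16 | 2.4% |

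Welch's test on the same comparison stays at 4.9% to 5.1% throughout. The omnibus F is at 5.3% to 6.8%.

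**5. Does a preliminary F test protect?** Not under the null that matters here, in which thiamine works and magnesium adds nothing. With combined = thiamine = 0.1433 and magnesium-only = 0 (37 per arm), the F test rejects in 90% to nearly 100% of trials. The follow-up comparison is then back at 11.0%, 7.5% and 3.4% for s_M of 0.02, 0.1214 and 0.2176.

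**6. Can any s_M make all three comparisons right?** By the formula in step 3, a pooled comparison is right only if the third arm's variance equals the average of the other two.
- Combined vs thiamine needs s_M = 0.176.
- Combined vs magnesium needs s_M² = 2(0.01474) − 0.04735, which is negative and so impossible.
- Thiamine vs magnesium needs s_M² = 2(0.04735) − 0.01474 = 0.07996, that is s_M = 0.283.

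So no single value serves. Over the range tried, combined vs magnesium runs at 6.9% to 8.9% and thiamine vs magnesium at 0.2% to 4.2%. At s_M = 0.176, where combined vs thiamine is exact, the other two are at 8.1% and 2.2%.

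**7. Price of not pooling.** If all SDs are 0.2176, n = 37 and the difference is 0.16, the noncentrality is 0.16/(0.2176 × √(2/37)) = 3.16. The noncentral t gives 88.0% power pooled (108 df) and 87.7% with two-arm variances (about 72 df); simulation gave 88.1% and 87.8%. With the pilot SDs, Welch's power for 0.16 is 97.0% at 37 per arm.

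**The case against.** The strongest reply is that the plan names only the omnibus F, and that test is close to its nominal level. The pairwise procedure behind the 2% to 11% is an assumption about what follows the F test. Had Tukey been used, combined vs thiamine would run at 5.7%, 3.4% and 1.2% for s_M of 0.02, 0.1214 and 0.2176 (37 per arm). This stands as a limit on the size of the point. It does not remove the point, because the primary objective cannot be answered without a pairwise estimate and the plan leaves the method open.

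A reader might infer that the 1.8-fold ratio of the pilot SDs (0.2176/0.1214 = 1.79) is what inflates the key comparison. It is not. With equal arms, a two-arm pooled t test at those SDs rejects in 5.0% to 5.2% of null trials. Conversely, with both thiamine-containing arms at 0.1214 and s_M = 0.02, the three-arm pooled comparison still rejects at 10.8%. The third arm's SD is the driver.

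A reader might also infer that the test is anti-conservative. That holds only for s_M below about 0.176. A small s_M is plausible, since this arm has had no Pabrinex at the 2-hour sample and the pilot group with the smaller mean change also had the smaller SD. It remains an assumption, and at the protocol's own planning SD the test is conservative.

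Finally, the pilot evidence is thin. The table does not say whether its values are absolute or relative changes, while section 4.4.1 defines the outcome as a relative change. The SDs rise with the means (SD/mean 0.68 and 0.85), so variances might be closer on another scale. If the pilot is the earlier study described in section 1.2, that study was not fully controlled. These points lower confidence in unequal variances, but they give no reason to assume equal ones.

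**Conclusion.** The point holds as a gap that is cheap to close, not as a fatal flaw. The plan names an equal-variance omnibus test and no method for the comparison that answers its primary question. If combined minus thiamine is tested on the three-arm mean square, unadjusted or F-protected, its type I error is about 2% to 11%, and the documents cannot say where in that range it falls or on which side of 5%. If the pilot SDs hold, at least two of the three pooled pairwise comparisons are off their nominal level whatever the magnesium-only SD.

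The documents do not support the stronger readings that the trial will run at 7.5% to 11%, that the named F test is invalid, or that pooling costs material power. On the last, at the protocol's 0.16 difference the thiamine vs magnesium comparison exceeds 99% power by either method when both SDs are 0.1214. The sample size is unaffected.

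The figures rest on normal data, equal arms, the pilot SDs taken as true and an assumed magnesium-only SD. Confidence is moderate.

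**What to change.** In the synopsis and section 8.2, replace the single-phrase method with three statements:
- Combined minus thiamine is the primary comparison.
- This difference and the other between-arm differences are each estimated with arm-specific variances: Welch t test and confidence interval, or robust or arm-specific residual variances if a regression model is used.
- If an omnibus test is kept, it is Welch's ANOVA. The three-arm mean square is not used for any two-arm comparison.

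The cost is a few lines of text, settled before analysis, with no further patients or samples. If the SDs are in truth equal, power for 0.16 at 37 per arm falls by about 0.3 points and stays well above the planned 80%.
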